- Number, date and time of logins
- Pages visited

We will use this data to describe:

- The proportion of people who register who make use of the DDPP (use to be defined during interviews with providers and document review)
- How people make initial use of the DDPP

If the usage data supplied by the providers contains the same referral ID as the minimum dataset, we will link the two datasets to address the following questions:

- What are the characteristics of those who access and make initial use of the DDPP?
- Do patterns of use vary by demographic characteristics (with a particular focus on determining the likely impact of these digital programmes on health inequalities)?

We will work with providers to ensure an opt-out consent process is in place for usage data by: 1) reviewing existing terms and conditions and consent statements that service users complete when registering to take part in the digital DPP, and 2) revising consent statements where necessary in conjunction with the provider. Service users need to be able to opt-out of their anonymised individual level data generated as part of their participation in the digital NHS DPP being used for an independent evaluation.

Once an agreed opt-out consent process is in place, we will ask all five providers for the first four weeks of usage data for all new registrants to the DDPP. Preferably, we are seeking individual-level user data to allow longitudinal analyses across the initial period of use (defined as the first 4 weeksfurther longitudinal analyses will be conducted by WP3). If this is deemed not feasible after discussion with a provider, we will seek median data.

We will ensure that the data transferred to UoM from the providers is anonymised and does not contain any personally identifiable data. Providers will be specifically requested to do the following before sending any usage data to UoM:

- Remove any personally identifiable data (name, contact details, DOB, medical records, IP address)
- Remove any address details leaving only the first 3 letters of the postcode, which will allow us to assess the geographical spread of usage data we obtain
- Review any free-text entries from service-users that risk sharing personally identifiable data
- Quality assurance

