We will request that providers encrypt the data files using an AES256 compliant encryption mechanism such as 7-zip. It will then be uploaded to a University of Manchester Dropbox for Business. The data will then be immediately moved from the Dropbox to a secure University of Manchester drive for storage. If this method is unfeasible for the provider due to technical issues, we will request that the data files are encrypted as above and sent to UoM by email with password shared by a separate communication.

Protocol v16.0 08/11/2021 IRAS ID: 220902 'Evaluating the NHS Diabetes Prevention Programme (NHS DPP)'

We will request specific research data storage from UoM IT for the usage data files. Data files will be then held on The University of Manchester secure server (and backed-up as per usual UoM standards) for the purposes of analyses and will only be accessed by the DIPLOMA team. We will request providers transfer data to us on a monthly basis using this process.

Analyses: Simple descriptive statistics will be used to analyse the MDS and describe the total number of people referred to the DDPP, the proportion of people referred who accept use of the DDPP, the characteristics of people referred and accepting use of the DDPP, the source of referrals, the providers referred to, the reasons (where applicable) that face to face education was declined, and the reasons (where applicable) for declining digital DPP and the duration between referral and registration to the DDPP.

Descriptive statistics will be used to calculate mean and standard deviation for the (or median and IQR if data are skewed) numbers of log-ins and other measures of use and describe the characteristics of those who access and make initial use of the DDPP. Tableau and other software programmes will be used to visualise the data on usage patterns, with a view to identifying patterns of use.

Logistic regressions will be conducted in order to determine whether patterns of use vary by demographic characteristics.

Amendment to WP9

Substantial amendment: [see documents: Amendment Tool, 16.12.20].

Rationale: In light of the new framework for the digital DPP, we are proposing an additional sub-study (WP9.3) relating to WP9, to explore patient experience of referral and engagement with the DDPP:

WP9.3: Qualitative interview study

Aim: Exploring patient experience of referral and engagement with the DDPP including:

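### WP 9.2's fallback of provider medians cannot yield the stated proportion of registrants who use the digital DPP, nor feed the planned logistic regressions

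*Protocol*

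**What the plan says.** All of this stands in the Protocol under Work package 9, Research question WP 9.2.

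- **Request.** The Methods say "we will ask all five providers for the first four weeks of usage data for all new registrants to the DDPP". The preferred form is stated too: "Preferably, we are seeking individual-level user data to allow longitudinal analyses across the initial period of use".
- **Fallback.** It is decided provider by provider: "If this is deemed not feasible after discussion with a provider, we will seek median data". No other aggregate is named.
- **Outputs from usage data.** The first is "The proportion of people who register who make use of the DDPP", with the definition of use still to be settled from provider interviews and document review. The second is how people make initial use.
- **Demographic questions.** These carry a condition: "If the usage data supplied by the providers contains the same referral ID as the minimum dataset, we will link the two datasets". One of them is "Do patterns of use vary by demographic characteristics", with a stated focus on health inequalities.
- **Analyses.** Log-ins are summarised by mean and standard deviation, or by median and IQR if skewed. For demographics: "Logistic regressions will be conducted in order to determine whether patterns of use vary by demographic characteristics". The referral-ID condition is not repeated there.

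Nothing says how a provider that supplies only medians enters the proportion or the regressions.

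**The concern.** The fallback asks for a statistic that does not match the outputs planned from the same data. A proportion needs a numerator and a denominator. A logistic regression needs person-level records or counts by covariate group. A provider median supplies none of these.

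A loss at provider level is also not a random loss. The WP 9.3 Setting paragraph says each local health service chose one of the five providers, so an unscored provider takes its areas with it. If those areas differ in deprivation or ethnicity, the usage proportion and the inequality comparison would describe a selected part of the programme. The form of the data is fixed at the request stage, so the right summary may be hard to recover once medians have been delivered.

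**Working it through.** The protocol gives no sample size, number of users or provider share for WP 9.2, so there is no figure of its own to reproduce. The check has four steps.

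**Inputs.** From the protocol: five providers, the median fallback, a proportion as the first output, and logistic regression. Assumed for illustration: use means at least one log-in in four weeks; provider shares *s*; and 70% use among the other providers.

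**1. Does a median determine the proportion?** Take 100 registrants in each constructed dataset.

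| Median log-ins | Proportions with any log-in that give this median |
|---|---|
| 3 | 51%, 60%, 75%, 90%, 100% |
| 0 | 0%, 10%, 25%, 49% |

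A median above 0 shows only that at least half used the programme; a median of 0 shows only that fewer than half did. The lower limit can be exactly 50%: with 50 registrants at 0 and 50 at 2 log-ins, the median is (0 + 2)/2 = 1.

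**2. Can provider medians be combined?** No. The median of a pooled group depends on the full distributions, so five provider medians, even with their denominators, do not give a programme median, mean or proportion.

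**3. Can a median enter the regression?** No. The stated route to demographics is linkage to the MDS by referral ID. A provider median has no person-level record and no referral ID. By contrast, for categorical covariates the logistic likelihood depends only on users and registrants in each covariate cell, so cross-classified counts would carry the same information.

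**4. How much is at stake?** If one median-only provider holds share *s* of registrants, all of that share is unscored.

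- Equal sizes (assumed): *s* = 1/5 = 20%; *k* such providers give *k* × 20%.
- Assumed split 40/25/15/12/8%: *s* runs from 8% to 40%.
- Assumed split 60/20/10/5/5%: *s* runs from 5% to 60%.

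With a median above 0, that provider's proportion lies between 0.5 and 1. The overall proportion is (1 − *s*) × 0.70 + *s* × (0.5 to 1), an interval of width 0.5*s*:

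| *s* (assumed) | Overall proportion | Width |
|---|---|---|
| 5% | 69.0% to 71.5% | 2.5 points |
| 20% | 66% to 76% | 10 points |
| 40% | 62% to 82% | 20 points |
| 60% | 58% to 88% | 30 points |

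The width does not depend on the assumed 70%.

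**The case against.** The strongest reply is that this is a contingency in a descriptive sub-study. Individual data on all new registrants are requested from all five providers, and the framework obliges providers to monitor usage. Nothing shows that the fallback will be used. The demographic questions already depend on a shared referral ID, and the requested usage fields hold no demographics, so unlinked individual records would lose that breakdown too. The outputs taken from the MDS (referrals, acceptance, characteristics of acceptors and the rest) are unaffected. A median does serve one planned summary, the median and IQR of skewed log-ins. WP 3 also requests usage data on a one-month cohort from each provider, although that request could meet the same obstacle. Finally, a provider that cannot export individual records may be unable to cross-classify use by ethnicity and deprivation.

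Most of this stands, and it limits the point. It does not rescue the fallback for the usage proportion, which carries no linkage condition.

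A reader might infer three stronger things that the protocol does not support:

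- **About a fifth of users is lost per such provider.** That is only 1/5 under an equal split, and no provider sizes are given.
- **Providers will refuse to share records.** The stated trigger is infeasibility after discussion.
- **The inequality analysis fails as a whole.** Linkable providers still contribute, and the protocol already foresees that some data may not link.

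**Conclusion.** The point holds in a limited form. Whenever the fallback is used, it cannot give the proportion of registrants who make use of the digital DPP, it cannot be pooled, and it cannot enter the regressions. All registrants of that provider are then missing from those outputs. Their share of the total is unknown: 20% if the five providers are equal, 5% to 60% under the unequal splits assumed here. For one such provider with a median above 0, the overall proportion is left uncertain by half its share, or 2.5 to 30 points over that range.

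This rests on use meaning at least one log-in. With a higher threshold, a median still shows only whether about half of registrants reach it. For the demographic analysis the added harm is smaller, because unlinkable data were already outside it. The matter is worth correcting because the change is small and a count is no less aggregate than a median.

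**What to change.** In the WP 9.2 Methods, replace the median fallback with a minimum aggregate from any provider for which individual data are not feasible:

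1. The number of new registrants and the number of them meeting the use definition in the first four weeks. Median and IQR of log-ins may be added but should not stand in for the counts.
2. Where the provider can do so, the same counts cross-classified by age band, sex, ethnic group and deprivation group, so that they can be pooled with the other providers in a grouped logistic regression.
3. A sentence on handling: providers supplying only overall counts enter the pooled proportion but not the demographic regressions. The Analyses paragraph should repeat that the regressions cover only providers with linkable records or cross-classified counts.

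The definition of use must be settled before the request is sent, since the count depends on it. The cost is a short change to the data request and a little more work for the provider. Small cells may need merging or suppression, and some providers may manage only item 1. That alone restores the proportion exactly.

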
On August 2018, the NHS DPP released a new framework for 'Healthier You: NHS Diabetes Prevention Programme'. The aim of the new framework is to expand the programme and to improve take-up and adherence to the DPP, including better targeting of the working age population and addressing delays associated with courses in rural areas.

The new framework also includes implementation of digital support for diabetes prevention alongside existing face-to-face provision, which has the potential to be one of the largest implementations of a digital programme in the NHS. Recruitment onto the new framework will start in August 2019, covering 45% of the sites in England, with the remaining 55% covered in 2020.

For operational reasons the DPP team re-procured the DPP intervention before the digital pilot could report. Therefore, the initial re-procurement focused mainly on face to face prevention programmes. However, all five of the new framework providers have been required to offer a digital prevention programme to people who decline invitation to the face-to-face programme. Once the results from the Digital DPP pilot are released, the DPP management team might decide to open up choice between face-to-face or digital intervention.

Aims and objectives

The overall aim of the DIPLOMA research programme is to provide a comprehensive assessment of the implementation, delivery and outcomes of the NHS DPP to inform commissioning.

The individual work package aims are as follows:

Work package 1 Access and Inequality

To assess whether sociodemographic factors influence access to the NHS DPP, and to explore the experience of patients and professionals in accessing the NHS DPP

Work package 2 Implementation

To assess the process of implementation of the NHS DPP, and explore the barriers and facilitators that affect the implementation of the NHS DPP

Work package 3 Service Delivery and Fidelity

To assess the theory, techniques and content of the NHS DPP, examine variation in delivery, and report the extent to which the NHS DPP is delivered with fidelity

Work package 4 Outcomes

To assess what outcomes participants achieve in the NHS DPP, and whether outcomes vary by services delivered and patient characteristics

Work package 5 Comparative Effectiveness

To assess whether the NHS DPP is more effective than usual care in reducing conversion of non-diabetic hyperglycaemia to diabetes, eventually reducing diabetes prevalence in England

Work package 6 External Validation

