The purpose of the scoping study is to identify factors that may influence access to NHS DPP, to help us design a questionnaire for the validation study. Method: we will use data from the qualitative interviews with patients and health professionals in the Access work package to identify important potential influences on access. We will use this to draw up suitable questions, in discussion with patients and clinicians on the Research Advisory Group. We anticipate that this is likely to include factors such as health status, comorbidities, motivation to improve health, health literacy and competing demands (e.g. employment, caring responsibilities).

Step 2: Questionnaire survey

We will undertake a short questionnaire survey of 400 patients (using post, telephone and online methods), to collect data on key patient factors (identified from the scoping study) that are likely to influence the offer and take-up of referral to the NHS DPP (i.e. whether 'NHS DPP referred' patients are referred to and attend the programme), but that are unavailable in routine datasets.

The purpose of the survey is:

- (a) To delineate the role psychological and social factors play in access inequalities, and identify factors potentially addressable by targeted interventions or programme modifications;
- (b) To determine the relative influence of and overall influence of these factors on participation;
- (c) To combine the results with analyses of CPRD, the minimum dataset, and other data sources to assess the extent to which associations between referral, programme attendance, and development of diabetes are confounded with patient characteristics and to adjust the associations for those factors.

The sample will consist of up to 30 patients from each of 20 practices. A suitable approach to sample size estimation for building regression models is to include 20 cases per parameter to be estimated. Our questionnaire includes 20 predictors (some of the questions will be combined into composites), giving us a recruitment target sample size of 400. To achieve this we are approaching a total of 600 patients.

Practices will produce a list of people at risk of diabetes who have been referred to DPP at least 3 months ago. After checking the list, practices will use a randomisation list provided by researchers to randomly select patients in a 1:1 ratio according to whether they are:

- (a) 'NHS DPP non-attenders', referred to NHS DPP but who did not attend any sessions

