Analyses: We will conduct a descriptive analysis of the engagement strategies and onboarding process reported in the framework response documents. We will conduct an analysis of the interview data relevant to this research question collected by work package 3, with the developers and providers of the interventions. We will undertake a directed content analysis approach² in order to identify pathways to referral, and strategies of onboarding. This analysis will be used to add depth of understanding to the document analysis and provide us with a comprehensive description of the intervention mechanisms in place to promote patient uptake as well as to help to inform our recruitment of patients and development of our patient interview topic guides.

Research question WP 9.2: To explore service user experience and patterns of engagement of the DDPP, using analysis of usage data.

Methods: Two datasets will be accessed to describe participant engagement with the DDPP. Data on the number of referrals and registrations to the DDPP and the characteristics of the participants who are offered and take up the DDPP will be collected from the NHS Diabetes Prevention Programme

_

² Hsieh H-F, Shannon SE. Three Approaches to Qualitative Content Analysis. Qualitative Health Research. 2005;15(9):1277-88.

Minimum Dataset (MDS), provided by NHS England. This dataset includes a referral ID, personal and demographic information, recruitment (to the DDPP) data, and clinical outcome data. We will use this dataset to describe:

- The total number of people referred to the DDPP
- The proportion of people referred who accept use of the DDPP
- The characteristics of people referred and accepting use of the DDPP
- The source of referrals
- The providers referred to
- The reasons (where applicable) that face to face education was declined
- The reasons (where applicable) for declining digital DPP
- Duration between referral and registration to the DDPP

Data on engagement with the DDPP will be collected from the providers of the DPP. According to the new framework for NHS DPP, providers must monitor service users' engagement with the service by collecting data on the amount, frequency, duration and depth of usage of the digital DPP e.g. viewing materials, completion of active elements, engaging with human coaches, inputting self-monitoring data and taking part in moderated sessions.

We will request data on:

- Individual logins (of app/website interface)

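### WP9.2 describes digital DPP uptake and referral-to-registration time without a follow-up horizon, so recent referrals in the extract would shorten the wait and, if kept in the denominator, lower the uptake

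*Protocol*

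**What the plan says.** Under Research question WP 9.2, Methods, the Protocol lists what will be described from the Minimum Dataset. Two items depend on elapsed time: "The proportion of people referred who accept use of the DDPP" and "Duration between referral and registration to the DDPP". Referral source and "The providers referred to" are listed as separate items.

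Under Analyses the method for the whole list is one sentence, beginning "Simple descriptive statistics will be used to analyse the MDS and describe the total number of people referred to the DDPP" and ending with "the duration between referral and registration to the DDPP". WP9.2 gives no data-cut date, no minimum time since referral, no time limit on acceptance and no rule for referrals whose outcome is not yet known.

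Start dates differed. The section on the digital programme says: "Recruitment onto the new framework will start in August 2019, covering 45% of the sites in England, with the remaining 55% covered in 2020". WP9.3 (Setting) says the re-procured programme was intended to cover all of England from August 2020, and that self-referral opened in that same month.

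Other work packages do deal with elapsed time. In WP6: "Practices will produce a list of people at risk of diabetes who have been referred to DPP at least 3 months ago". WP5.2 design 1 adds Cox and competing-risks models to its logistic models so as to handle censoring and deaths.

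**The concern.** A referral-to-registration time exists only for someone who has registered by the day the data are extracted. Among people referred shortly before that day, only the quick ones have registered. A plain mean or median of the recorded times is therefore right-truncated and too short for as long as referrals keep arriving. The uptake proportion has the matching problem: people still deciding sit in a denominator of everyone referred, but cannot yet be in the numerator.

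Both effects are stronger where the window of referrals before the cut is shorter, for example for self-referral or for sites that joined in 2020. If uptake or waits were broken down by referral source or provider, part of any difference could reflect observation time and not the service. WP9 is meant to lead to recommendations on how to maximise engagement, and uptake and waiting time are natural inputs to those.

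**Working it through.** The Protocol states no wait, uptake or data cut for WP9.2, so there is no figure to reproduce. The check shows the direction of the bias and how its size depends on assumptions.

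**Assumed model.** Referrals arrive evenly over a window of W weeks ending at the cut. Among people who will eventually register, the wait is exponential with mean m weeks. For a referral made c weeks before the cut, the chance of having registered is 1 − e^(−c/m). Averaging over c from 0 to W gives:

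- Share of eventual acceptors counted: S = 1 − (m/W)(1 − e^(−W/m))
- Observed mean wait: M = {m − [2m² − (2m² + mW)e^(−W/m)]/W} / S

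**Windows.** This version of the Protocol is dated 08/11/2021. Taking the cut near that date (an assumption), a start in August 2020 gives about 15 months, 15 × 52/12 = 65 weeks. A start in August 2019 gives about 27 months, 27 × 52/12 = 117 weeks.

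**Waits.** Means of 4 and 8 weeks are assumed.

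**Worked case, m = 8, W = 65.** e^(−65/8) = 0.0003.
- S = 1 − (8/65)(0.9997) = 0.877
- Numerator of M = 8 − [128 − 648 × 0.0003]/65 = 6.03
- M = 6.03/0.877 = 6.88 weeks, and 6.88/8 − 1 = −14%

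| True mean wait m | Window W | Eventual acceptors counted | Observed mean wait | Error in mean wait |
|---|---|---|---|---|
| 4 weeks | 65 weeks | 94% | 3.74 weeks | −7% |
| 4 weeks | 117 weeks | 97% | 3.86 weeks | −4% |
| 8 weeks | 65 weeks | 88% | 6.88 weeks | −14% |
| 8 weeks | 117 weeks | 93% | 7.41 weeks | −7% |

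Between the two windows, for identical services, the gap is about 3 to 5 percentage points of eventual acceptors and 0.1 to 0.5 weeks of mean wait.

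**Short windows, for contrast.** No date in the Protocol points to these.

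| True mean wait m | Window W | Eventual acceptors counted | Observed mean wait |
|---|---|---|---|
| 4 weeks | 13 weeks | 70% | 2.5 weeks |
| 4 weeks | 26 weeks | 85% | 3.3 weeks |
| 4 weeks | 52 weeks | 92% | 3.7 weeks |
| 8 weeks | 13 weeks | 51% | 3.3 weeks |
| 8 weeks | 26 weeks | 70% | 5.1 weeks |
| 8 weeks | 52 weeks | 85% | 6.6 weeks |

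The direction is the same throughout. The size falls quickly as the window lengthens relative to the wait.

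**The case against.** The strongest reply is that the Protocol is silent on open referrals. It does not say that they are ignored, dropped or counted as refusals. A cut date and a denominator rule are the kind of detail often left to an analysis plan, and a percentage registered within a fixed time is itself a simple descriptive statistic that the plan's wording does not rule out. If open referrals were left out of the denominator, uptake would not necessarily be too low.

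That is right as far as it goes, and a reader should not infer that the plan has decided to ignore open referrals. What remains is that the one method named, applied as written to these two items, gives a truncated wait, and the stated denominator is people referred. WP6 and WP5 put their handling of elapsed time in the Protocol itself, so it is reasonable to ask the same of WP9.2.

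A second reply concerns reach. A reader might infer that start date alone could produce the differences between sites or providers. The Protocol does not support that. It plans no table of uptake or wait by site, provider or referral source, and it ties no provider to a start tranche. The logistic regressions in WP9.2 concern patterns of use, taken over the first four weeks after registration, and are not affected.

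A third reply is that steady intake and a single exponential wait are crude. Referral rules changed during Covid-19, the 20% cap was lifted, and under self-referral and the practice-letter route people approach the provider themselves. This stands against the exact figures, but not against the direction for the wait. If the changes raised later intake, more referrals would lie near the cut and the bias would be larger than shown.

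**Conclusion.** The point holds as a minor one. With recent referrals in the extract, the observed referral-to-registration time is too short. Uptake is too low if open referrals stay in the denominator. Both errors grow as the referral window shortens, and would matter if results were broken down by referral source or provider.

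The size depends on two things the Protocol does not give: the cut date and the wait distribution. Under the assumptions set out above, it is small to moderate for windows of 65 to 117 weeks. It is tempting to say that about half of eventual acceptors would be missed. That needs a window of about 13 weeks with a mean wait of 8 weeks, and nothing in the Protocol supports so short a window.

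The outputs affected are descriptive. The comparative effectiveness analysis in WP5 does not rest on them.

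**What to change.** State the data cut in WP9.2, and adopt one of two reporting rules:

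1. **Fixed horizon.** Report the percentage registered within a set time of referral, for example 12 weeks, among referrals with at least that much follow-up. Summarise time to registration in the same set, up to the same horizon. This is a defined quantity, not eventual uptake: under the exponential model, 12 weeks captures 1 − e^(−12/4) = 95% of eventual acceptors when the mean wait is 4 weeks and 1 − e^(−12/8) = 78% when it is 8 weeks.
2. **Cumulative incidence.** Estimate the cumulative incidence of registration from referral, with unresolved referrals censored at the cut, and read the percentage registered and the time to registration from that curve. Treat decline as a competing event if decline dates are held. The Protocol mentions reasons for declining but no date, so otherwise keep decliners in the analysis as not registered.

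Use the same rule for any breakdown by referral source or provider.

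The cost is small. Both options use the referral and registration dates that the planned duration already needs. The downside is that the most recent referrals are excluded under the first option and contribute only partial follow-up under the second.
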